## Assessing an animal-assisted treatment program for adults with aphasia: the Persons with Aphasia Training Dogs (PATD) Program

with a second SLP not involved in PATD training. All individuals who collect and code data are trained by the PI.

Preliminary data: The four participants who have completed the program responded to the PATD Satisfaction Survey (see appendix). Average ratings were: 'better dog training skills'= 4.25 (range 2-5), 'more opportunities to socialize'= 4 (range 2-5), 'more opportunities to communicate'= 3.25 (range 1-5), 'more confidence'= 3.75 (range 2-5). Consistent with the hypothesized mechanisms of action for AAT, all participants responded 'Yes' that they 'had more confidence' and were 'communicating more frequently'.

## PARTICIPANTS

The study population is persons who have aphasia consequent to cerebro-vascular accident CVA) who are a minimum of six months post-onset.

### Eligibility/Inclusion criteria:

To participate individuals must have aphasia resulting from CVA, those who have had multiple strokes, subcortical strokes, or who have crossed aphasia, are not explicitly excluded. . All participants must meet the following criteria: 1) be aged 21 years or older, 2) have English as a native or primary language, 3) evidence of having the linguistic and cognitive capacity to understand the research requirements, 4) demonstrate the willingness and stamina to participate in the protocol, 5) be negative for diagnosis of neurological injury or disease other than CVA. 6) reside within approximately 1 hour drive from MRRI ([name]) and/or PSPCA ([name]). Participants may have concomitant medical conditions such as heart disease, or diabetes, but at the time of participation they will be medically and neurologically stable, such that they can participate in this multiple session protocol. Participants will be characterized relative to demographic (e.g., age, education-level) and stroke-related (e.g., time post onset, presence of hemiplegia) variables. To determine aphasia type and severity, participants will complete the *Western Aphasia Battery-Revised* (Kertesz, 2006) in week 1.

Participants will be included without respect to gender, race or ethnic background. Pregnant women and Einstein employees/students will be neither targeted nor specifically excluded. Children (persons under the age of 21) are excluded from this study as the aims of this project are relevant to the study of acquired aphasia in adults.

### Recruitment

A minimum of twenty participants with chronic (> 6 months post) stroke-aphasia will be enrolled. Participants will be recruited from the MRRI Research Participant Registry and through additional venues. The MRRI Research Participant Registry is a database of individuals who have previously consented to being contacted regarding research opportunities (Schwartz et al., 2005). The database includes approximately 302 individuals with stroke-aphasia, with an average of 43 enrollees each year, who have self-selected for interest in research participation. Additional recruitment strategies will include use of IRB approved fliers, which may be posted on websites, social media (e.g., ARCH, Aphasia Recovery Connection, or Poems in Speech Facebook pages) included in newsletters (e.g., the Aphasia Resource Collaboration Hub), shared with individuals who have previously expressed interest in the PATD program, and provided to internal (Jefferson Moss-Magee Rehabilitation) and local community-based speech-language pathologists who work with people with stroke-to share with their clients. The study may also be posted on the Thomas Jefferson University Clinical Trials Finder and study staff may present information about the study at internal (Jefferson Moss-Magee Rehabilitation) and local community aphasia-groups and events. Recruitment will also occur using the Recruitment Enhancement Services provided by the Jefferson Clinical Research Institute at Thomas Jefferson University. Recruitment Enhancement Service (RES) provides assistance to the principal investigator in developing the study's recruitment plan and may assist in identifying and contacting potential participants using the Informatics group, internal communication resources, community contacts, and other available resources as outlined in the study team's protocol. MyChart may also be used to identify and generate lists of potential participants. Individuals identified by the RES as meeting eligibility criteria will be contacted by either postal mail or email.

## Assessing an animal-assisted treatment program for adults with aphasia: the Persons with Aphasia Training Dogs (PATD) Program

Participants will be informed that they may withdraw from the study at any time, without penalty, and contact personnel are provided on the consent form. Participants will be informed that they can contact the PI at a later time if they would like to spend time reviewing the information in order to avoid them feeling pressured to participate. They will also be informed that pre- or post-consent screening or behavioral test results may indicate that they are not eligible to continue with the study. Pre-consent, research candidates from outside of the MRRI Research Registry will be screened to confirm diagnosis and related medical information and for geographic eligibility.

Assignment into each arm will be done using block randomization with stratification. Interested participants will be screened for one of two strata: 1) participation with a family dog or 2) participation through the Pennsylvania SPCA (PSPCA). Interested participants will be automatically assigned to the PSPCA condition if a) they do not have a family dog or b) their family dog is not eligible to participate. There will be no minimum requirement for assignment into either stratum.. As participants are enrolled in either the PATD or PATD-PSPCA condition, they will be block randomized into either immediate or waitlist treatment groups. Recruitment will be ongoing, until a minimum of ten PATD immediate and ten PATD waitlist participants have been enrolled.

**Retention plan:** Strategies to encourage retention will include: 1) The timeline of the study will be detailed in recruitment and consent materials to indicate that multiple sessions are required for the study and that there will be a lag period between some phases of the study. 2) Scheduling of assessment and training sessions will be done, to the maximum extent possible, at the convenience of study participants. Assistance with travel arrangements to attend assessment sessions may be offered, Moss Rehabilitation Research Institute contracts with third-party vendors for this purpose. 3) Participants will be informed that they may continue or enroll in standard of care rehabilitation or therapy during the duration of their participation, but will be asked to inform study staff of any changes. 4) Participants will be asked to not enroll in any other research activities through completion of the immediate post training evaluations (with the speech-language pathologist and with the dog trainer). and will be asked to not enroll or participate in any other dog training activities for the duration of the study through the follow-up evaluations. 5) Participants will be informed at enrollment of the timeline for participation.

**Study Timeline:** Lesson plans consistent with the example in figure 1 have been written for all target obedience behaviors and validated with four participants with aphasia. Additional training and evaluation materials have been developed and piloted with these participants by the PI. Certified SLPs will have prior experience with PWA such that any training required on battery instruments will be minimal and will not delay data collection. CPDTs are positive reinforcement practitioners and have consulted with the PI on the lesson plans and adapted *PPAHE*. From the study start date (date of first enrolled participant) recruitment, enrollment will continue through week 72 of the study to provide sufficient time for later enrolled participants to complete either protocol. Data collection and analysis will be ongoing, with preliminary dissemination of findings anticipated to begin once enrollment has ended.

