## RESEARCH DESIGN AND METHODS

### Study Procedures and Materials

Cognitive-linguistic and psychosocial assessment sessions for all groups will take place at the Moss Rehabilitation Research Institute. Participants will complete either 3 (immediate arms) or 4 (delayed arms) assessment (dx) sessions over the course of either 19 or 25 weeks, respectively (Table 1); we anticipate that each assessment session will take approximately three hours to complete. The instruments included in these assessments will be the *Assessment of Living with Aphasia* (Simmons-Mackie et al., 2014), the PATD-program ALA supplement (developed by the PI for this study, not administered in pretraining evaluation(s)) the *Confidence after Stroke Measure* (Horne et al., 2017), and the *Behavioural Assessment of Dysexecutive Syndrome* (Wilson et al., 1996). Participants will also complete at baseline the *Western Aphasia Battery-Revised* (WAB-R, Kertesz, 2006) to provide a profile of their aphasia. The WAB-R will not be repeated.

Assessing an animal-assisted treatment program for adults with aphasia:  
the Persons with Aphasia Training Dogs (PATD) Program

All participants will be evaluated before training begins, immediately following training, and at a 3-month follow-up. Participants in the delayed arm will participate in two pre-training evaluations, one immediately upon enrollment and one at the end of the delay period immediately before beginning training.

Week	1	2	3	4	5	6	7	8	9	10	11	12	13	
Immediate	Pre-training eval.	Skill 1	Skill 2	Skill 3	Skill 4	Skill 5	Post-training eval.							Follow-up eval. (week 19)
Waitlist	Pre-training eval.						Pre-training eval.	Skill 1	Skill 2	Skill 3	Skill 4	Skill 5	Post Training eval.	Follow-up eval. (week 25)

Table 1: Sequence of participation

PATD training sessions will take place either at participants' homes, for those working with a family dog, or at the PSPCA. Training sessions that take place at the PSPCA will occur in an enclosed room, in an open indoor space in which the dog is tethered or on-leash, or in a fenced-in outdoor yard.

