All sessions will be video-recorded. A section of the informed consent is dedicated to explaining the use & storage of recordings. An optional sharing of recorded information for educational purposes is also included in the consent.

Due to the variable nature of the timeline for PSPCA volunteer onboarding and to preserve the timeline of study activities, participants who choose to participate as PSPCA volunteers will be asked to complete volunteer training/onboarding before beginning other study activities. Once onboarding is completed, the participants’ first assessment session will be scheduled and study activities will proceed accordingly.

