Participants interested in working with PSPCA dogs are required to successfully complete the official PSPCA volunteer orientation before beginning the PATD program, hence they must be independently approved by a representative of the PSPCA to be able to work with shelter dogs. Much of the orientation involves hands-on demonstration and practice, making it accessible to individuals with aphasia. Participants interested in volunteering at the PSPCA must demonstrate sufficient mobility and strength to handle a dog. Risks associated with travel to and from the PSPCA are anticipated to be not more than those associated with urban daily life.

Confidentiality

In any research study, there is the risk that personal data will become inappropriately known (risk of loss of confidentiality). Data will be coded with a participant ID number that has no connection with the participant's name or other identifying information. The master list containing the link between the data and the identity will be password protected and accessible only to study personnel. All physical information will be stored in locked drawers in the locked office of the PI or the PI's locked testing room at Moss Rehabilitation Research Institute to which other study staff will have access. Electronic data will be stored on AEHN/TJU networks and/or OneDrive, password-protected computers, , or encrypted external memory devices as appropriate. Data will be removed from the memory storage of the video-recording device as soon as it is practicably possible to transfer it to these systems. Immediately after transfer the videos will be removed from the video-camera storage.

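### Nothing in the plan delays randomisation or disclosure of the arm until after the baseline self-reports, and for shelter participants the order of enrolment, randomisation and onboarding is not settled

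*Combined protocol and SAP*

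**What the plan says.** **Allocation.** The Recruitment section fixes the stratum (family dog or PSPCA shelter dog) by screening people who express interest, and then states: "As participants are enrolled in either the PATD or PATD-PSPCA condition, they will be block randomized into either immediate or waitlist treatment groups". Recruitment runs until at least ten people per arm are enrolled. Feasibility Metrics counts consent and enrolment as one step and lists no separate count of people randomised.

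**Disclosure.** The Retention plan says "The timeline of the study will be detailed in recruitment and consent materials" and, as a separate item, "Participants will be informed at enrollment of the timeline for participation". The timeline differs by arm: "Participants will complete either 3 (immediate arms) or 4 (delayed arms) assessment (dx) sessions over the course of either 19 or 25 weeks, respectively" (Study Procedures and Materials).

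**Baseline.** Outcome Measurement/Participation Timeline and Study Procedures and Materials both place the waitlist arm's first evaluation straight after enrolment. The ALA and the Confidence after Stroke Measure are part of that evaluation.

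**Shelter onboarding.** Under Study Procedures and Materials, "participants who choose to participate as PSPCA volunteers will be asked to complete volunteer training/onboarding before beginning other study activities". After that, the "first assessment session will be scheduled and study activities will proceed accordingly". The Dog-training risk text adds that "they must be independently approved by a representative of the PSPCA to be able to work with shelter dogs".

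**Late ineligibility.** Candidates are told that "pre- or post-consent screening or behavioral test results may indicate that they are not eligible to continue with the study".

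**The concern.** The ALA and the Confidence after Stroke Measure are self-reports of confidence, participation and well-being. Someone who has just learned that training starts next week may answer differently from someone who has just learned of a six-week wait. If the arm is known at week 1, the baseline is no longer a measurement taken before allocation. In the immediate arm it is also the only pre-training score available for the main Aim 2 estimate, the mean pre-to-post change in each ALA domain.

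The second issue is confined to the shelter stratum. Onboarding is of variable length and needs outside approval. If people are randomised before it, those who do not clear it leave the randomised set with no baseline score, yet they have already counted toward the target of ten per arm. The plan gives no rule for them. One purpose of randomising here is to learn whether a waitlist design is workable in a larger trial, so the sequence needs to be defined.

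**Working it through.** The plan states no figure on this point, so the check starts by putting the texts in order.

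**1. Sequence in both strata.**
- Consent and enrolment are one step (Feasibility Metrics).
- Allocation happens as people are enrolled (Recruitment).
- The timeline is given at enrolment (Retention plan).
- The first evaluation follows enrolment (Participation Timeline).

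The plain reading is: consent and enrolment, randomisation, timeline told, week-1 evaluation. No text moves randomisation or its disclosure to after week 1, and none describes allocation concealment. One link is inferred: that the timeline told at enrolment is the person's own. The general timeline is already in the recruitment and consent materials, so the later item adds little unless it is arm-specific.

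**2. Sequence in the shelter stratum.** Two readings are open.
- *Enrolment at consent, then onboarding.* This fits the joint count of consent and enrolment, the setting of strata by screening, and the word 'other' in the onboarding text, which suggests that onboarding is itself an activity of people already in the study. It also fits PSPCA approval being a condition for starting the programme rather than for randomisation. It does not fit a first evaluation straight after enrolment, because onboarding of variable length lies between.
- *Onboarding, then enrolment.* This fits a first evaluation straight after enrolment, and randomisation could be one of the activities that wait for onboarding. It does not fit the joint count of consent and enrolment.

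The first reading is the likelier. Neither is stated.

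**3. Where an arm-aware baseline enters.** Write the pooled mean change as D = (n_I × d_I + n_W × d_W) / (n_I + n_W), with n_I = n_W = 10. If knowing the arm shifts the immediate arm's week-1 score by b, then d_I shifts by −b and D by −b × 10/20 = −0.5b. For scale, the 90% half-width for D at n = 20 is 1.729/√20 = 0.387 SD of the changes. A shift as large as that half-width would need b = 0.387/0.5 ≈ 0.77 SD. The documents give neither the size nor the direction of b. For the waitlist arm the plan does not say which of its two pre-training scores is used. If it is the week-1 score, an arm-aware shift could enter there as well.

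The between-arm analysis is the difference in ALA domain scores at week 7, with no change score or baseline covariate written. The week-1 score does not enter it.

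**4. Losses, if randomisation precedes onboarding.** The documents give neither the number of shelter participants nor a failure rate. The following is assumption only.
- With 5, 10 or 15 of 20 in the shelter stratum and 10% to 30% not clearing onboarding, expected losses run from 5 × 0.10 = 0.5 to 15 × 0.30 = 4.5 people.
- The week-7 90% half-width is t(0.95, n1+n2−2) × √(1/n1 + 1/n2), in SD units: 0.775 for 10 vs 10, 0.828 for 10 vs 8, and 0.881 for 8 vs 8.
- Four losses would leave 16/20 = 80%. If retention is computed on those enrolled, that misses the hypothesis of above 80% before any training has taken place.

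**The case against.** The strongest reply is that the plan never says shelter participants are randomised before onboarding, nor that the timeline given at enrolment is the allocated one. Both points stand. For shelter participants the defect is an unsettled order, and arm-aware baselines are something the plan permits rather than something it prescribes.

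Losses are also partly provided for. The number completing baseline and the withdrawals are tracked, the targets are minimums, and enrolment stays open through week 72, so a shortfall could be made good. That stands too, but a count is not a rule for how such people are analysed, and the stopping target is still expressed in people enrolled.

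A reader might infer more than the documents support:
- *That onboarding losses would undo the randomisation.* Onboarding is the same in both arms, approval is independent, and the investigator does not identify study participants to PSPCA staff. Rejection has no evident route to depend on arm; only voluntary abandonment could.
- *That all 20 baselines are given with the arm known.* This needs the disclosure to be arm-specific, which is not stated.
- *That the week-7 comparison is distorted through baseline.* As written it uses no baseline score, and it is labelled exploratory. Week-7 answers are given knowing the arm in any open waitlist design, and a later randomisation would not change that.
- *That post-consent ineligibility necessarily means no baseline data.* The aphasia battery is itself given in week 1, so some data may exist.
- *That waitlisted shelter participants will be exposed by volunteering with dogs while they wait.* Nothing says they will, orientation precedes week 1 in both arms, and other dog training is already ruled out.

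**Conclusion.** The point holds as a gap in sequence. On the plain reading, allocation and the timeline come before the week-1 self-reports, and nothing prevents baseline from being given knowing the arm. The consequence falls on the main pre-to-post ALA change, through the immediate arm's only pre-training score, at half of whatever shift occurs in that arm (assuming ten of 20). That shift cannot be sized from the documents.

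For shelter participants the passages on enrolment, first evaluation and onboarding need reconciling. Loss after randomisation follows only if randomisation comes first, and its size is unknown; the range of 0.5 to 4.5 people rests wholly on assumed stratum sizes and failure rates.

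This is a cheap improvement. Confidence is moderate to high on baseline awareness and moderate on onboarding losses.

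**What to change.** Amend Outcome Measurement/Participation Timeline, Recruitment, the Retention plan and Study Procedures and Materials so that they give one order:

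1. At consent, describe both possible timelines.
2. Confirm eligibility; in the shelter stratum, complete PSPCA onboarding and approval.
3. Complete the week-1 assessment.
4. Randomise within stratum, and only then disclose the allocated timeline.

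Count the ten per arm at randomisation. In the flow diagram, show people who do not clear onboarding, or are found ineligible after consent, as losses before randomisation.

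This needs wording only and no extra visit. The cost is tighter scheduling: with the evaluation in week 1 and Skill 1 in week 2, immediate-arm participants learn their start only about a week ahead.

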## RESEARCH DESIGN AND METHODS

### Study Procedures and Materials

Cognitive-linguistic and psychosocial assessment sessions for all groups will take place at the Moss Rehabilitation Research Institute. Participants will complete either 3 (immediate arms) or 4 (delayed arms) assessment (dx) sessions over the course of either 19 or 25 weeks, respectively (Table 1); we anticipate that each assessment session will take approximately three hours to complete. The instruments included in these assessments will be the *Assessment of Living with Aphasia* (Simmons-Mackie et al., 2014), the PATD-program ALA supplement (developed by the PI for this study, not administered in pretraining evaluation(s)) the *Confidence after Stroke Measure* (Horne et al., 2017), and the *Behavioural Assessment of Dysexecutive Syndrome* (Wilson et al., 1996). Participants will also complete at baseline the *Western Aphasia Battery-Revised* (WAB-R, Kertesz, 2006) to provide a profile of their aphasia. The WAB-R will not be repeated.

Assessing an animal-assisted treatment program for adults with aphasia:  
the Persons with Aphasia Training Dogs (PATD) Program

All participants will be evaluated before training begins, immediately following training, and at a 3-month follow-up. Participants in the delayed arm will participate in two pre-training evaluations, one immediately upon enrollment and one at the end of the delay period immediately before beginning training.

Week	1	2	3	4	5	6	7	8	9	10	11	12	13	
Immediate	Pre-training eval.	Skill 1	Skill 2	Skill 3	Skill 4	Skill 5	Post-training eval.							Follow-up eval. (week 19)
Waitlist	Pre-training eval.						Pre-training eval.	Skill 1	Skill 2	Skill 3	Skill 4	Skill 5	Post Training eval.	Follow-up eval. (week 25)

Table 1: Sequence of participation

PATD training sessions will take place either at participants' homes, for those working with a family dog, or at the PSPCA. Training sessions that take place at the PSPCA will occur in an enclosed room, in an open indoor space in which the dog is tethered or on-leash, or in a fenced-in outdoor yard.

Participants enrolled in the PATD program will engage in five approximately once-weekly individual training sessions with the PI, either with a family dog (PATD) or by volunteering at a local shelter, the Pennsylvania SPCA (PATD-PSPCA). Each session will be dedicated to one of five pre-determined, sequentially-presented, obedience skills (i.e., LOOK, TOUCH, SIT, STAY, COME). Training sessions will last a maximum of 75 minutes, with an additional half hour allotted to the beginning of the first training session (before the dog begins participation) to review principles of positive-reinforcement training. Sessions may last for fewer than 75 minutes if a) criterion is achieved, b) human or dog participant demonstrates fatigue, loss of attention, etc. Subsequent sessions will begin with a brief probe of the participant's skill in cueing the dog to perform the behavior trained the previous week. Following the probe, sessions will continue with a review of that week's lesson plan, after which the PI will model the first training step three times. After the model has been provided, the participant will attempt the procedure, receiving instructive feedback or reinforcement from the trainer. Instruction will proceed to the subsequent step when the participant and dog have attained 5 successful trials at the current step. The same demonstration procedure will be used at each subsequent step. Commands will be trained using one hand gesture for each behavior. To mark behaviors, participants will use a clicker attached to a wrist band, which can be hand-held or allowed to dangle for ease of use for those with hemiplegia. Participants will have the option of introducing the verbal command, but will not be required to do so. All participants will be asked to provide their dog with a walk before training sessions to support the dog in being ready to participate. The PI will demonstrate the steps of the obedience training and will be present for the entire training session to observe, assist, and provide feedback to participants. Within the framework above, treatment will be individualized for each participant-handler/dog pairing based on real-time clinical decision-making. One goal of positive reinforcement training is relationship building between the particular handler/dog pairing. Reinforcement, redirection, and feedback will be provided by the PI, who will complete all training sessions, based on the individual needs of the human and dog participants. Participant handlers will be provided with feedback regarding their use of shaping, timing of cues and rewards in real time and lesson plans will be modified as needed for each individual. Examples of lesson plan modifications include training in use of one hand for those with hemiplegia or increased white space or font size or additional pictographs for those with reading difficulty.

Participants will be encouraged to practice the skill in 3 practice sessions over the course of the week. Participants will be instructed that each practice session should not last longer than approximately 30 minutes and that breaks for play, drinking water, sniffing-walks, should be provided as needed. Practice sessions may also be broken up into shorter increments (e.g., three 10-minute sessions, six 5-minute sessions). Practice will be used as a measure of participant compliance. PATD-participants will be provided with aphasia-friendly written materials including: 1) lessons plans, 2) practice log sheets, and 3) practice reminders. They may also be provided with example videos of the PI performing the obedience skills with her own dog. PATD-participants will be informed that at the beginning of the subsequent training session, the PI will be evaluating their ability to cue the behavior introduced the previous week using a PI-adapted *Pet Partners® Animal-Handler Evaluation*

Assessing an animal-assisted treatment program for adults with aphasia:  
the Persons with Aphasia Training Dogs (PATD) Program

(adapted *PPAHE*) will be used to rate handler cueing on a scale of 0 (“not ready”) to 2 (“best”). Progression to training of each behavioral skill will not be contingent on evaluation of the previous skill.

After each training session, the participant will be provided with a copy of the appropriate lesson plan, three participant practice logs, and, if interested, a video demonstrating the PI performing the target skill with her own dog. As study staff will not be present for practice sessions, participants will be instructed on behaviors to watch for that indicate the dog might need/want a break or to stop practice for the day, e.g., signs of fatigue (e.g., inattention, disinterest in interaction) or distress (e.g., tail tuck, ears flat/back, avoidance). PSPCA participants will be instructed to practice with the same dog with whom they trained on each skill. If that dog is not available, they will be instructed to work with another dog who has been labeled by PSPCA staff to be at (or easier than) their current level of proficiency as determined by the PSPCA (e.g., beginner volunteers may only work with beginner-appropriate dogs).

All sessions will be video-recorded. A section of the informed consent is dedicated to explaining the use & storage of recordings. An optional sharing of recorded information for educational purposes is also included in the consent.

Due to the variable nature of the timeline for PSPCA volunteer onboarding and to preserve the timeline of study activities, participants who choose to participate as PSPCA volunteers will be asked to complete volunteer training/onboarding before beginning other study activities. Once onboarding is completed, the participants’ first assessment session will be scheduled and study activities will proceed accordingly.

